2.7 Imaging Studies to Determine Early Response to Therapy in Soft Tissue Sarcoma

Chemotherapy may improve the chance for a cure in patients with high risk sarcomas (intermediate to high grade, ≥ 5 cm), but does not benefit every patient and is associated with toxicities.[3,4] Identifying sarcoma patients who are likely to benefit from neoadjuvant and/or adjuvant systemic treatment has been challenging. In most current trials of anticancer drugs, the objective radiographic response of tumor to treatment, as defined by the international Response Evaluation Criteria in Solid Tumors (RECIST), is used as a surrogate measure for therapeutic benefit.[45] The assessment of soft tissue sarcoma response to chemotherapy is difficult, however, because sarcomas are heterogeneous tumors and consist of varying degrees of cellularity, fibrous septa, stroma, and necrosis. The beneficial effects of a therapy which is successful at eradicating neoplastic cells may be masked by a tumor mass that does not shrink or even grows due to necrosis or intratumoral hemorrhage.[46] Standard radiologic response defined by a change in the size of the tumor to preoperative chemotherapy has not correlated consistently with histologic results at surgery or with survival.[47-49]

FDG-PET: Positron emission tomography (PET) using 18F-fluorodeoxyglucose (FDG), is a tool for evaluation of treatment response in sarcoma. In neoadjuvant therapy for high grade localized sarcomas, serial FDG-PET is a sensitive method to assess early response to therapy; pretreatment standardized uptake value (SUV) and change in SUV predict outcome.[50,51] Eary and colleagues first used FDG-PET in sarcomas and demonstrated the relationship between the quantitative value of the FDG metabolic rate of tumor and the semi-quantitative measure of tumor uptake, the SUV.[52] Eary and colleagues showed that a higher tumor maximum SUV at diagnosis correlated with a greater risk for disease progression and death from disease in patients with soft tissue or bone sarcomas.[50] In a later study, Schuetze and colleagues found that the pretreatment tumor maximum SUV and change in maximum SUV after neoadjuvant chemotherapy independently identified

sarcoma patients at high risk of tumor recurrence.[51] Forty-six patients with high-grade localized extremity sarcomas were studied. Those with a baseline tumor maximum SUV of 6 or greater and less than a 40% decrease in FDG uptake after chemotherapy were at high risk for systemic disease recurrence, estimated to be 90% at 4 years. In contrast, those whose tumors had a 40% or more decline in the tumor maximum SUV after chemotherapy, were at significantly lower risk of recurrent disease and death following surgery and radiation. Interestingly, in this study the histologic response to chemotherapy did not correlate with patient outcome.

In this randomized study subjects will undergo baseline staging scans including FDG-PET. After the 14 day Run-in period of pazopanib versus placebo, and prior to commencement of preoperative chemotherapy, subjects will undergo repeat FDG-PET. After 2 cycles of chemotherapy FDG-PET will be repeated.

If results of this trial can be confirmed in larger trials, then this could establish that changes in tumor SUV in response to antiangiogenic therapy and to chemotherapy may distinguish those patients who are likely to benefit from these systemic therapies from those who will not.

2.8 Risks/Benefits

Subjects will have a 2:1 chance of being randomized to receive pre-operative pazopanib during a Run-in period. The potential benefits include early assessment of response to antiangiogenic therapy and possible enhanced tumor cell kill. Subjects who respond to pazopanib during the Run-in period (defined in **Section 11.3**) will have the option to continue pazopanib for one year, following surgical resection of their tumor.

Antiangiogenic therapy may improve outcome for patients with high risk resectable soft tissue sarcoma, but this remains unproven. Benefits of chemotherapy include a potential improvement in disease free survival and overall survival compared to no systemic therapy. Risks of the study include side effects associated with pazopanib and with chemotherapy as described in **Section 10**.

3.0 STUDY OBJECTIVES

3.1 Primary Objectives

- To determine the absolute values and changes in standardized uptake values (SUV) by FDG PET before and after a 14 day Run-in period of pazopanib versus placebo, and to compare this to the change in SUV following pre-operative chemotherapy.
- To evaluate the correlation between antiangiogenic activity and pazopanib drug exposure.
- To assess the response rate by RECIST criteria after the 14 day Run-in period of pazopanib versus placebo and compare this to the response rate following pre-operative chemotherapy.

3.2 Secondary Objectives

- To examine the activity of antiangiogenic therapy with pazopanib combined with pre-operative chemotherapy for high risk extremity soft tissue sarcomas as measured by: Histological necrosis at surgery
Change in plasma and tumor biomarker assays of angiogenesis
- To evaluate the safety of sequential treatment with pazopanib and pre-operative chemotherapy with doxorubicin and ifosfamide.

4.0 STUDY DESIGN

4.1 Description of Study

This is a multi-center randomized blinded study with 2:1 randomization of pazopanib versus placebo prior to neoadjuvant chemotherapy with doxorubicin and ifosfamide for adult soft tissue extremity sarcomas.

4.2 Endpoints

4.2.1 Primary Endpoints

- Absolute values and changes in standardized uptake values (SUV) of tumors measured by FDG-PET pre- and post receipt of pazopanib versus placebo, and post receipt of 2 cycles of preoperative chemotherapy
- Tumor response by RECIST criteria
- Correlation of pazopanib trough concentration with the change in SUV from FDG PET and change in RECIST measurements on MRIs

4.2.2 Secondary Endpoints

- Safety profile
- Pathologic response at the time of surgery as measured by % tumor viability
- Progression free survival and overall survival
- Change in plasma and tumor angiogenic biomarker levels pre- and postneoadjuvant therapy.

4.3 Study Procedures

The study procedures outlined in Appendix A are discussed in this section, with the exception of Treatment (**Section 7**). Screening will occur within approximately 14 days prior (unless otherwise noted) to the first day of dosing (pazopanib versus placebo, Run-in period, Day 1). For procedures performed at Screening and repeated, the later procedure performed prior to dosing will serve as a baseline for clinical assessment.

Informed Consent

Signed informed consent will be obtained from the subject or the subject's legally acceptable representative by the principal investigator or a co-investigator (the "Investigator") before any study-specific procedures are undertaken.

The Investigator or his/her representative will explain the nature of the study to the subject, and answer all questions regarding this study. Prior to any study-related screening procedures being performed on the subject, the informed consent statement will be reviewed, signed, and dated by the subject and by the person who administered the informed consent. A copy of the informed consent form will be given to the subject and the original will be placed in the subject's research chart.

Research analysis of plasma samples and surgical tumor tissue will be performed once the subject has signed and dated the informed consent, approved by the IRB of record, after the nature of the testing has been explained and the subject has had the opportunity to ask questions. The informed consent must be signed before the testing is performed or tumor tissue and plasma samples are used for analysis.

Medical History

The following information will be collected during the Screening Visit:

- Complete medical history, including documentation of any clinically significant medical condition
- Oncology history, including primary cancer diagnosis
 - Pathology of primary tumor
 - Stage of tumor (location, size, grade and depth)

At each visit, the subject's medical history will be reviewed and any changes from baseline will be recorded. On Run-in period, Day 1 any changes observed from the screening assessments, prior to dosing, will be recorded in the subject's medical history. All medication (prescription or over-the-counter, including vitamins and/or herbal supplements) will be recorded beginning with the Screening Visit and continued for the duration of the study.

Physical Examination

A complete physical examination will be performed at Screening, including height. A symptom-directed physical examination including weight will be performed at all other visits unless indicated otherwise. Clinically significant physical examination findings after the administration of the first day of dosing will be recorded as adverse events.

12-lead Electrocardiogram (ECG)

A resting 12-lead ECG will be performed at the Screening Visit, unless performed for standard of care within 14 days. The investigator or a designee will sign and date the ECGs, determine if any findings outside normal physiological variation are clinically significant (in consultation with a cardiologist if necessary), and document this on the ECG report. ECGs will also be performed at the initiation of pazopanib maintenance therapy, Cycle 1 Day 1 and Cycle 2 Day 2.

Vital Signs

Vital sign determinations of heart rate, blood pressure and body temperature will be measured at all visits unless indicated otherwise.

Pregnancy Test

For female subjects of childbearing potential, a serum pregnancy test will be performed at the Screening Visit and a urine pregnancy test will be done at the Run-in period Day 1 visit prior to the first dose of pazopanib versus placebo. Subjects considered not of childbearing potential must be documented as being surgically sterile or post-menopausal (for at least 1 year). The test results must be reviewed and determined to be negative prior to dosing. If the urine pregnancy test is positive at Cycle 1 Day 1, it should be confirmed by a serum pregnancy test. The test may be repeated at the discretion of the Investigator at any time during the study. Should the subject become pregnant or suspect she is pregnant while participating in this study, she should inform the Investigator immediately. The Principal Investigator should be notified and will be responsible for contacting the representative at Novartis.

Clinical Laboratory Tests

All subjects will undergo the laboratory assessments outlined in **Appendix A**. After Cycle 1 Day 1, clinical laboratory tests should be performed within 72 hours surrounding the scheduled study visit date. Any laboratory value outside the reference range that is considered clinically significant by the investigator will be followed as appropriate. Clinically significant laboratory values will be recorded as adverse events if they meet the criteria as specified in **Section 7.7**.

Tumor Assessments (Radiologic)

Baseline staging scans including a positron emission tomograph with a built-in CT component (FDG-PET), MRI of the primary tumor, and diagnostic CT chest are required at Screening (within approximately 14 days of the Run-in Period, Day 1). After the 14-day Run-in period of pazopanib versus placebo, and prior to commencement of preoperative chemotherapy, subjects will undergo repeat FDG-PET and MRI of the primary tumor. After 2 cycles of chemotherapy, FDG-PET and MRI of the primary tumor will be repeated.

CT of the chest without contrast will be performed approximately every 3 months for the first year following surgery and MRI (or CT) of the primary site of the tumor will be performed every 6 months.

ECOG Performance Status

The ECOG performance status will be assessed at Screening, Run-in Period Day 1 and Day 1 of each subsequent cycle, Final Visit, and at the 30-day Follow-up Visit. See **Appendix B** for ECOG criteria.

Pharmacokinetic Studies

Trough level (22-24 hrs after pazopanib dosing): A blood sample (4 mL K2EDTA purple top blood collection tube) will be drawn to assess the trough plasma pazopanib concentration during the 14 day Run-in period of pazopanib monotherapy, after completion of adjuvant chemotherapy, and every 3 months thereafter until completion of pazopanib maintenance therapy. During the Run-in period, the trough level will be drawn twice during Days 10 through 14: 1) one trough on any of Days 10-14 and 2) on the day of the FDG PET after the Run-in period, 22-24 hours after the patient's last dose of pazopanib versus placebo. After completion of surgery/adjuvant chemotherapy, the trough will be drawn once during each of the following periods: 1) Week 2 (Days 10-15 after restarting pazopanib), Weeks 3-4 after

restarting pazopanib, and then every 3 months for 1 year). If all trough levels are drawn, a total of 8 samples are possible in a single subject.

An optional full intensive pharmacokinetic visit will be performed in consenting patients during Weeks 2-4 in subjects following surgery/adjuvant chemotherapy. Blood (4 mL K2EDTA purple top blood collection tube) will be obtained at the following timepoints: immediately before pazopanib dosing (within 5 minutes before giving pazopanib on the day of PK dosing) and 1, 2, 3, 4, 6, 8 hour timepoints (+/- 10 minutes), and 24 hrs (range 22 to 24 hours) after dosing (a total of 8 samples/subject).

Biomarker Studies

Plasma will be collected for measurement of VEGF and soluble VEGFR2 (sVEGFR2) at baseline, after the 14 day Run-in period of pazopanib, after completion of neoadjuvant chemotherapy and approximately every 3 months thereafter until completion of pazopanib maintenance therapy, when indicated. Quantitative enzyme-linked immunosorbent assays (ELISA) for VEGF and sVEGFR2 will be performed on plasma and tumor extracts.

Plasma will also be collected for micro RNA at baseline, after the 14 day Run-in period of pazopanib, following neoadjuvant chemotherapy and every 3 months thereafter until completion of pazopanib maintenance therapy, when indicated.

5.0 SUBJECT SELECTION

5.1 Inclusion Criteria

- 5.1.a Histologically or cytologically confirmed soft-tissue sarcoma, excluding alveolar and embryonal rhabdomyosarcoma, well- and dedifferentiated adipocytic sarcomas, Ewing's, osteosarcoma, or gastrointestinal stromal tumor. AJCC (6th Edition) Stage III or T2a Stage II or Stage IV-treatment naive patients planned for resection of the primary tumor, with resectable metastatic disease.
- 5.1.b Measurable disease greater than 5 centimeters in greatest dimension. Measurable lesions are defined as those that can be accurately measured in at least one dimension (longest diameter for non-nodal lesions and short axis for nodal lesions to be recorded) by chest x-ray, CT scan, MRI or with calipers by clinical exam. All tumor measurements must be recorded in millimeters (or decimal fractions of centimeters).
- 5.1.c Intermediate or high grade lesions: 2 or 3 on a scale of 1-3 or grades 2 to 4 on a scale of 1-4.
- 5.1.d Sarcoma located on upper (includes shoulder) or lower (includes hip) extremities or on the body wall.
- 5.1.e Life expectancy of greater than 6 months.
- 5.1.f ECOG performance status ≤ 1 (Karnofsky $\geq 80\%$; see **Appendix B**).

- 5.1.g No prior chemotherapy, radiotherapy, or antiangiogenic therapy.
- 5.1.h Age \geq 18 years
- 5.1.i No significant organ dysfunction with initial labs:

ANC	\geq 1500 / μ L
Hgb	\geq 9.0 g/dL
Platelets	\geq 100,000 / μ L
Creatinine	\leq 1.5 x ULN
Bilirubin	\leq 1.5 mg/dL
AST/ALT	\leq 1.5 x ULN

PT/INR/PTT within 1.2 X the upper limit of normal unless a subject is receiving Coumadin and has stable INR which is in range for the desired level of anticoagulation
- 5.1.j Normal cardiac function: LVEF \geq 50%
- 5.1.k Blood pressure (BP) no greater than 140 mmHg (systolic) and 90 mmHg (diastolic) for eligibility. Initiation or adjustment of BP medication is permitted prior to study entry provided that the average of three BP readings on baseline assessment prior to enrollment is less than 140/90 mmHg.
- 5.1.l Eligibility of subjects receiving any medications or substances known to affect or with the potential to affect the activity or pharmacokinetics of pazopanib will be determined following review of their cases by the Principal Investigator (see **Section 7.4** for further information).
- 5.1.m Women of child-bearing potential and men must agree to use adequate contraception.
- 5.1.n A female is eligible to enter and participate in this study if she is of non-childbearing potential (i.e., physiologically incapable of becoming pregnant) or if she is of childbearing potential, if she fits the criteria in **Appendix C**.
- 5.1.o Ability to understand and the willingness to sign a written informed consent document.

5.2. Exclusion Criteria

- 5.2.a Subjects with known brain metastases and/or unresectable sarcoma.
- 5.2.b Uncontrolled intercurrent illness including, active serious infection, symptomatic congestive heart failure, unstable angina pectoris, cardiac ventricular arrhythmia requiring anti-arrhythmic therapy, serious hepatic impairment, or psychiatric illness/social situations that would limit compliance with study.
- 5.2.c Pregnant or lactating women.
- 5.2.d Subjects with no additional active malignancy within the last 3 years.

- 5.2.e Subjects receiving other investigational agents.
- 5.2.f Subjects with a history of allergic reactions attributed to compounds of similar chemical or biologic composition to pazopanib or other agents used in the study.
- 5.2.g Subjects who have both bilirubin >ULN *and* AST/ALT >ULN
- 5.2.h Subjects with a urine protein/creatinine ratio greater than 1.
- 5.2.i Subjects with a baseline QTc of equal to or greater than 480 msec or other significant ECG abnormalities.
- 5.2.k Certain medications that act through the CYP450 system are specifically prohibited in subjects receiving pazopanib and others should be avoided or administered with extreme caution and require PI approval.
 - **Strong inhibitors of CYP3A4** such as ketoconazole, itraconazole, clarithromycin, atazanavir, indinavir, nefazodone, nelfinavir, ritonavir, saquinavir, telithromycin, voriconazole may increase pazopanib concentrations and are prohibited. Grapefruit juice is also an inhibitor of CYP450 and should not be taken with pazopanib.
 - **Strong inducers of CYP3A4**, such as rifampin, may decrease pazopanib concentrations, are prohibited. (See **Section 7.2**)
 - Medications which have narrow therapeutic windows and are substrates of CYP3A4, CYP2D6, or CYP2C8 should be avoided and, if necessary, administered with caution. (See **Section 7.2**)

A list of medications that are specifically prohibited or those that should be used with caution during this trial of pazopanib can be found in **Section 7.2**. Comprehensive lists of agents that could affect pazopanib through the cytochrome P450 system can be found in **Appendix D**.

Pazopanib, 800 mg once daily, has no effect on CYP2C9, CYP1A2, or CYP2C19 *in vivo* but does *in vitro*. Therefore, therapeutic doses of warfarin, a substrate of CYP2C9, and omeprazole, a substrate of CYP2C19 are permitted. Caffeine, a substrate of CYP1A2, is also permitted.

- 5.2.l Certain medications that are associated with a risk for QTc prolongation and/or Torsades de Pointes, although not prohibited, should be avoided or replaced with medications that do not carry these risks, if possible. Comprehensive lists of agents that are associated with a risk for QTc prolongation and/or Torsades de Pointes can be found in **Appendix E**.
- 5.2.m Subjects who require heparin other than low-molecular weight heparin

5.2.n Subjects with any condition that may impair the ability to swallow or absorb oral medications/investigational product including:

- any lesion, whether induced by tumor, radiation or other conditions, which makes it difficult to swallow capsules or pills
- prior surgical procedures affecting absorption including, but not limited to major resection of stomach or small bowel
- active peptic ulcer disease, not on a proton pump inhibitor
- malabsorption syndrome

5.2.o Subjects with any condition that may increase the risk of gastrointestinal bleeding or gastrointestinal perforation, including

- active peptic ulcer disease, not on a proton pump inhibitor
- known intraluminal metastatic lesions
- inflammatory bowel disease (e.g., ulcerative colitis, Crohn's disease) or
- other gastrointestinal conditions which increase the risk of perforation
- history of abdominal fistula, gastrointestinal perforation or intra-abdominal abscess within 28 days prior to beginning study treatment

5.2.p Subjects with any of the following cardiovascular conditions within the past 6 months

- cerebrovascular accident (CVA) or transient ischemic attack (TIA)
- cardiac arrhythmia
- admission for unstable angina
- cardiac angioplasty or stenting
- coronary artery bypass graft surgery
- pulmonary embolism, untreated deep venous thrombosis (DVT) or DVT which has been treated with therapeutic anticoagulation for less than 6 weeks
- arterial thrombosis
- symptomatic peripheral vascular disease.
- Class III or IV heart failure as defined by the NYHA functional classification system. A subject who has a history of Class II heart failure and is asymptomatic on treatment may be considered eligible.

5.2.q History of hemoptysis in excess of 2.5 mL (1/2 teaspoon) within 8 weeks prior to first dose of study drug

5.2.r History of serious or non-healing wound, ulcer, or bone fracture.

5.2.s HIV-positive subjects on combination antiretroviral therapy are ineligible because of the potential for pharmacokinetic interactions with pazopanib.

5.2.t Subjects with severe hepatic impairment

- Bilirubin $>3 \times$ ULN, regardless of any level of ALT

6.0 SUBJECT REGISTRATION AND RANDOMIZATION

All subjects will be registered by the coordinating center (University of Washington) and entered into the Protocol Accrual Tracking System (PATS). Information regarding the PATS system is available at http://www.cancerconsortium.org/rto/protocol_office/pats/. A complete, signed study consent and HIPAA consent are required for registration. An Investigator must review and sign the eligibility list for patients enrolled on the trial.

This is a double-blinded study. Patients will be randomized 2:1 to receive pazopanib versus placebo by the SCCA Investigator Drug Supply (IDS) Pharmacy according to a computer program from randomization.com. Physicians, research study staff, and patients will be blinded from the time of enrollment until the time of the patient's surgery, when unblinding will occur.

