G Pazopanib may be resumed 1 week after completion of post-operative therapy (chemotherapy +/- radiation) for those randomized to the treatment who had a response by imaging, to be continued for 1 year. Unblinding occurs during the first post-op visit after surgery.

H PEG-Filgrastim should be administered approximately 24-48 hours after completing chemotherapy. 10 days of filgrastim may be substituted.

I Mesna will be given at 400 mg/m². Post IFOS doses will be at 4 hours and 8 hours (+/- standard clinical dosing windows)

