11.3.3 Pathologic Response at Surgery

All specimens of primary tumor will be examined for pathologic response at the time of surgery. The study pathologist will estimate the amount of viable tumor, and report the percentage of necrosis. For purpose of analysis, tumors will be classified as either ≥95% necrosis or <95% necrosis.

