Descriptive displays of preliminary clinical endpoints (pathologic response, progression-free survival, overall survival) will compare response for the pazopanib and placebo groups, and will investigate the relationship between early pharmacodynamic response (by PET) and clinical endpoints. Response of high-risk soft tissue sarcoma to neoadjuvant chemoradiation therapy was estimated as 52% (38% no residual tumor, 14% ≥ 95 pathologic necrosis) in a series of 496 patients.[9] A smaller series found only 13/46 (28%) with $< 10\%$ viable tumor in surgical specimens following a variety of neoadjuvant regimens.[51] To direct planning of future studies, we will measure the rate of complete pathological response defined as greater than 95% necrosis in the surgical excision specimen. A 90% Wilson (score) binomial confidence interval will be computed for the rate of complete pathological response.

There are no stopping rules planned for toxicity, but safety will be monitored continuously. All subjects who are registered and receive at least one dose of study drug will be included in the safety analysis.

All reported adverse events will be coded using the Cancer Therapy Evaluation Program (CTEP) Common Toxicity Criteria version 4.0. The number and percent of subjects reporting adverse events (all, severe or worse, serious and related) will be quantified. Listings will be provided for all on-study deaths and adverse events that lead to withdrawal from study. Narratives of all serious adverse events and deaths on-study will be provided.

Correlative study assays will be analyzed using descriptive statistics, generally comparing pazopanib and placebo groups. Correlation will also be evaluated between pazopanib trough concentrations and drug exposure over the dosing interval (area-under-the-concentration-curve, AUC) in subjects consenting to the full intensive pharmacokinetic visits.

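### Sections 6.0 and 7.0 open the treatment code at different times, the necrosis read need not be recorded first, and 11.3.3 and 14.1 use different necrosis cut-offs

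*Combined protocol and SAP*

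**What the plan says.** On the blind:

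- Section 6.0 says "Physicians, research study staff, and patients will be blinded from the time of enrollment" and continues "until the time of the patient's surgery, when unblinding will occur".
- Section 7.0, footnote G to the treatment table, says "Unblinding occurs during the first post-op visit after surgery". The same footnote reserves maintenance pazopanib for patients randomized to it who responded on imaging, so the arm has to be known by then.

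On the necrosis read:

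- Section 11.3.3 says "All specimens of primary tumor will be examined for pathologic response at the time of surgery" and "The study pathologist will estimate the amount of viable tumor, and report the percentage of necrosis". It does not mention masking and does not place the read before or after unblinding.
- Appendix A marks pathology review in the surgery column, also without reference to the code.

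On the cut-off:

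- Section 11.3.3: "tumors will be classified as either ≥95% necrosis or <95% necrosis".
- Section 14.1: "complete pathological response defined as greater than 95% necrosis in the surgical excision specimen".
- Section 14.1 cites as a benchmark a 496-patient series with 52% response, made up of "38% no residual tumor, 14% ≥ 95 pathologic necrosis". Section 2.1 gives the prognostic rationale in the same inclusive form, 95% necrosis or more.

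**The concern.** Percent necrosis is a visual estimate, and a reader who knows the arm can be influenced by it. The trial has a placebo and a double blind, but the text does not secure that blind for this endpoint. Section 6.0 lifts it at the operation that produces the specimen. Footnote G lifts it later without linking the date to the read.

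The cut-off matters for a different reason. Section 14.1 sets the response rate beside an inclusive benchmark but defines its own rate exclusively, so a tumor at exactly 95% is placed differently by two sections of one protocol.

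Section 1.0 names tumor necrosis as one of the two measures in the pilot hypothesis. Section 14.1 compares pathologic response between the arms descriptively and uses the rate to guide later trials. An estimate influenced by knowledge of the arm, or a rate counted by a different rule from its benchmark, would carry into that planning.

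**Working it through.** **1. Order of read and unblinding.** No arithmetic applies, so the two texts are followed in turn.

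- *Following 6.0.* The code opens at surgery. The specimen does not exist before surgery, and 11.3.3 and Appendix A also place the examination at surgery. The read and the code-break are tied to the same event with no order between them. The read can therefore be made with the arm known.
- *Following footnote G.* The code opens at the first postoperative visit. With the examination placed at surgery, the natural order is read first, code second. But neither footnote G, 11.3.3 nor Appendix A makes a recorded percentage a condition for opening the code.
- *Who is masked.* A study pathologist may fall under the physicians or the research staff in 6.0. That does not settle the matter, because the 6.0 blind ends for all these groups at surgery.

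**2. The plan's own benchmark figures.**

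- First series: 38% + 14% = 52%, as stated. The 14% band starts at 95% inclusive.
- Second series: 13/46 = 28%, as stated. It is defined by less than 10% viable tumor. If necrosis and viable tumor are complements (an assumption), that means more than 90% necrosis, which matches neither 11.3.3 nor 14.1.

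**3. What the cut-off can change.** The two rules differ only for tumors read at exactly 95%. If k of n tumors have that reading, the 14.1 rate is lower than the 11.3.3 rate by k/n; it can never be higher.

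Inputs: n = 21 and 2:1 allocation (14.2). Patients withdrawn before surgery are replaced (7.8), so about 21 specimens are planned. If allocation lands at 2:1, the arms have 21 × 2/3 = 14 and 21 × 1/3 = 7.

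For k = 1:

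- all patients: 1/21 = 4.8 points
- pazopanib: 1/14 = 7.1 points
- placebo: 1/7 = 14.3 points

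The documents give no frequency for readings of exactly 95% and no rounding rule, so k cannot be derived.

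**4. Scale against the planned precision.** Section 14.1 plans a 90% Wilson interval, (p + z²/2n ± z√[p(1−p)/n + z²/4n²]) / (1 + z²/n), with z = 1.645. Illustrative counts near the 28% benchmark:

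- 6/21: p = 0.286; (0.286 + 0.064)/1.129 = 0.310, half-width 0.155; interval 15.6% to 46.5%.
- 7/21: p = 0.333; (0.333 + 0.064)/1.129 = 0.352, half-width 0.160; interval 19.2% to 51.3%.

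One reclassified tumor shifts the estimate by 4.8 points against an interval about 31 points wide (46.5 − 15.6 = 30.9).

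**The case against.** The best defence reads the passages together. Section 6.0 may only name the stage at which the blind ends, with footnote G as the operational rule. Examination at surgery followed by unblinding at a later visit then gives the right order. The pathologist plausibly belongs to a blinded group, no passage sends the assignment to pathology, and the use the documents show for the code after surgery is the maintenance decision. The endpoint is secondary (4.2.2), its arm comparison is descriptive, and no test or decision rule depends on it. The percentage itself is reported, so either cut-off can be applied afterwards.

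Much of this stands. A reader might infer that the necrosis read is unprotected whichever text is followed. The documents do not support that: under footnote G the order is implied, and only the explicit requirement is missing. A reader might also infer that the arm comparison will be biased. That does not follow either, because nothing shows that the pathologist learns the arm, and the size and direction of any bias cannot be derived.

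The defence does not remove the conflict. Section 6.0 is the section that sets out the blinding, its wording gives a different event from footnote G, and nothing says which governs. A site that follows 6.0 complies with the protocol and may still read the specimen with the code open.

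**Conclusion.** The point holds, with limited weight. The two unblinding times conflict. Under 6.0 the read can be made with the arm known; under footnote G it is implied to come first but not required to be recorded first. The necrosis cut-offs also conflict, and the 14.1 wording departs from 11.3.3, from the rationale in 2.1 and from the 52% benchmark. It would be too strong to say that it departs from every benchmark in 14.1, since the second one matches neither rule.

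Each tumor at exactly 95% is worth 4.8, 7.1 or 14.3 points for denominators of 21, 14 and 7, assuming all planned specimens are obtained and allocation lands at 2:1. How many there will be is unknown. The cut-off slip is recoverable from the recorded percentages. An unmasked read is harder to undo: a masked re-read is not ruled out, but none is planned.

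The primary comparison should not be drawn into this. The day-14 scans are acquired well before surgery, while the blind is in force under either text.

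**What to change.** - Give one unblinding time in both 6.0 and footnote G. Set it after the necrosis percentage has been read masked to arm and locked, and before the arm is needed for the maintenance decision.
- State in 11.3.3 that the study pathologist is masked to treatment assignment.
- Use at least 95% necrosis in both 11.3.3 and 14.1.

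The cost is a few wording changes and a code-release step at the pharmacy that waits for the locked read. The assignment is disclosed slightly later. Where no postoperative therapy is given, the read has to be completed promptly so that the maintenance decision is not held up. Sample size, visits and the primary analysis do not change.
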